Symptom questionnaires will be collected at an enrollment visit (V1), and participants will be randomly assigned to the EI or DI groups. For those in the EI group, the intervention will begin 0-7 days thereafter. Sessions will be administered over 10 business days. Follow-up data collections will be obtained at 2 weeks following enrollment (V2) [0-14 days after completion of the intervention for the early intervention group], and 4-7 weeks after the V2 (V3, primary outcome). Following V3, those in the DI group will be offered the opportunity to cross over to receive 4 CR intervention sessions and will continue to be followed for data collections at 0-14 days (V4) after completing their sessions, and 4-7 weeks (V5) after V4. Mean contrasts will be used to compare the changes in measures of perceived stress (PSS) from V1 to V3, the primary outcome, in the early vs. delayed intervention groups. Similar analysis will occur for secondary outcomes.

Background, Rationale, and Context:

Background:

Abnormal electroencephalographic (EEG) asymmetries have been reported in a variety of neurological, cardiovascular, and psychophysiological conditions including insomnia, attention deficit hyperactivity disorder (ADHD), anxiety, autism spectrum disorders, depression, dyslexia, post-traumatic stress disorder (PTSD), and traumatic brain injury (TBI) (Avram, Baltes, Miclea, & Miu, 2010; T. S. Hale et al., 2010; Hale et al., 2009; T.S. Hale et al., 2010; Kemp et al., 2010; Lazarev, Pontes, Mitrofanov, & deAzevedo, 2010; Marzano, Ferrara, Sforza, & De, 2008; Metzger et al., 2004; Moscovitch et al., 2011; Rabe, Beauducel, Zollner, Maercker, & Karl, 2006; Riemann et al., 2010; Spironelli, Penolazzi, & Angrilli, 2008; Stroganova et al., 2007; Thibodeau, Jorgensen, & Kim, 2006; Wolynczyk-Gmaj & Szelenberger, 2011). Many, if not all of these conditions are associated with autonomic imbalance and

psychophysiological dysfunction manifested as low heart rate variability or other abnormal measures (Beckham et al., 2003; H. Cohen et al., 2000; Katz-Leurer, Rotem, Keren, & Meyer, 2010; Spiegelhalder et al., 2011; Tobaldini et al., 2013).

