- Current, significant symptoms of long-COVID.
- Current medical student.

Participants will be asked to report use of alcohol, recreational drugs, CBD products, chiropractic, cranial-sacral therapy, and bio-energy work during the intervention, and until V3 and then for the crossover group at V4 and V5.

Sample Size:

Up to 166 participants might be enrolled to get the target sample of 138 to complete intervention. With this target sample size, the study will have 80% power with alpha of 0.05 to detect a clinically meaningful change in the perceived stress scale of 3 points, assuming PSS standard deviation similar to our Cereset Research exploratory study preliminary data (SD 5.62 for difference in PSS from V1 to V3). The clinically meaningful change of 3 points on the PSS was selected based on literature regarding clinically meaningful change in this scale, clinical experience of the investigators, and because this magnitude of change, if detected, would be clinically significant enough to warrant clinical implementation as the immediate next step. The selected target difference in the primary outcome is slightly higher than a minimally important difference of 2.19 to 2.66 points(Drachev et al., 2020), but it is greater than an established clinically relevant difference of 4 points demonstrated in a clinical sample(Plantinga, Lim, Bowling, & Drenkard, 2017). In addition to evaluating the primary question about whether the intervention results in a 3 point improvement in PSS scores at 4-7 weeks post intervention compared to waitlist controls, the study will also explore for potential targets for future research, including those taking selected medications, and those with comorbid conditions or symptoms of interest.

Intervention and Interactions:

Participants will be randomly assigned to either an Early Intervention (EI) group which will receive 4 CR sessions of audible tones echoing current brainwave activity following enrollment, or a Delayed

Intervention (DI) group which will continue current care only and will serve as a control group through the V3 follow-up visit. Participants in both groups will continue their other current care throughout the study.

Schedule of Activities

		Intervention (4 Sessions over 10 calendar days)		Post Interventio	n Data Collection	Crossover Intervention (4 sessions over 10 calendar days)		on)	Crossover Post Inter (DI gr	vention Data Collection oup oly)			

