Event	Enrollment (V1) Baseline Data Collection	Baseline Recording and Session 1 (E1) { Within 0-7 days of V1 }	Session 2 (E2)	Session 3 (E3)	Session 4 (E4)	Post Intevention (V2) Data Collection {Within 0-14 days of E4/10-21 days post enrollment}	Post Intervention (V3) Data Collection {Within 4-7 weeks of V2}	Crossover Baseline Recording and Session 1 (D1) {Within 3 months of V3}	Crossover Session 2 (D2)	Crossover Session 3 (D3)	Crossover Session 4 (D4)	Post Intervention (V4) Data Collection {Within 0-14 days of final D4 Intervention}	Post Intervention (V5) Data Collection {Within 4-7 weeks of (V4) data collection}
Informed consent	х												
Demographics	х												
Perceived Stress Scale (PSS) - Standard	х						x						х
Perceived Stress Scale (PSS) - Since last data collection						x						x	
Insomnia Severity Index (ISI) - Standard	х						x						х
Insomnia Severity Index (ISI) - Since Since last data collection						x						X	
Center for Epidemiological Studies Depression Scale (CES-D)						x	x					x	х
Generalized Anxiety Disorder 7-Item (GAD-7) - Standard							x						х
Generalized Anxiety Disorder 7-Item (GAD-7) - Since last data collection						x						x	
PTSD Checklist for Civilians (PCL-C) - Standard	х						x						х
PTSD Checklist for Civilians (PCL-C) - Since Since last data collection						х						x	
Fatigue Severity Scale (FSS)	x					х	x					х	х
Quality of Life Scale (QOLS)	х					х	x					х	х
Interpersonal Support Evaluation List (ISEL-12)	х					x	x					х	х
Multiple Ability Self-Report Questionnaire (MASQ)	х					x	x					х	х
Depression, Anxiety, and Stress Scale (DASS-21)	х					x	x					х	х
EQ-5D Self-Report Health State Question	х					x	x					х	х
WHO's Heath and Work Performance Questionnaire (HPQ)	х						x						х
Healthcare Utilization	х						x						х
COVID Questions	х					x	x					x	x
COVID Healthcare Worker Study Barriers to Participation Survey							x						х
FAROS HRV Recording	x					x	x					x	х
Randomized {EI=Early Intervention DI=Delayed Intervention }	х												
Cereset Research Intervention		X	Х	х	Х			Х	х	х	х		
Study Coordinator Data Entry	х					х	x					x	х
Technologist Data Entry		X	X	X	Х			Х	X	х	Х		

Cereset Research – COVID-19 Study Flow Chart:

Crossover DI Group

Crossover:		V4 Within 0-14 days of final		V5 Within 4-7 weeks of V4
-Short baseline recording		intervention session (up to 45 minutes)		(up to 45 minutes)

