Data will be analyzed using the most recent versions of SAS (SAS Institute, Inc., Cary, NC) or the R Statistical Computing Environment. Histograms and descriptive statistics will be examined to evaluate the distribution of study outcomes. Mean contrasts will be used to compare the changes in symptom scores for the primary outcome of Perceived Stress Scale from V1 to V3 in the early intervention vs. delayed intervention groups, as well as secondary and exploratory outcomes/symptom scores. Linear mixed models, which can accommodate within-subject correlations due to repeated assessments over time, may also be used to generate point estimates for effect size along with 95% confidence intervals to support a future larger study if the results in this study do not support immediate clinical application, and potentially for other studies examining other outcomes or potentially more select samples. The association of outcome measures with baseline participant characteristics will also be explored.

Human Subjects Protection:

Subject Recruitment Methods:

Subjects will be recruited by physician referral, word of mouth, and through advertisement (elevator ads, posters, flyers, table outside cafeteria, video overview of study, etc.).

Informed Consent:

The research staff will obtain written informed consent or assent from each competent subject.

Subject Communication Methods:

Participants will be contacted by phone, email, and texting during the study. The study team is going to explore texting for appointment reminders and rescheduling.

Videoconference Data Collection Visit Alternative:

During this time of COVID-19, institutionally approved videoconferencing platforms might be used to interact with study subjects. In person visits are preferred, but in case of office closures or safety reasons the study team might collect data collections through REDCap and videoconferencing.

Confidentiality and Privacy:

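### The primary contrast of PSS change names no baseline covariate; ANCOVA on the V1 PSS already collected would cut variance by about 10–15% (pilot sampling range about 3–31%) at almost no cost

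*Combined protocol and SAP*

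**What the plan says.** The Analytical Plan states: "Mean contrasts will be used to compare the changes in symptom scores for the primary outcome of Perceived Stress Scale from V1 to V3", between the early and delayed intervention groups. The Abstract says the same: "Mean contrasts will be used to compare the changes in measures of perceived stress (PSS) from V1 to V3, the primary outcome". Neither names a covariate. The Analytical Plan adds that linear mixed models "may also be used to generate point estimates for effect size along with 95% confidence intervals", which makes them optional and leaves their handling of baseline open. Associations between outcomes and baseline characteristics are exploratory only.

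The covariate is already available. The Abstract says: "Symptom questionnaires will be collected at an enrollment visit (V1), and participants will be randomly assigned to the EI or DI groups". In the Schedule of Activities the row "Perceived Stress Scale (PSS) - Standard" is marked at both V1 and V3, so the two scores come from the same form.

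The Sample Size section plans on the change score ("SD 5.62 for difference in PSS from V1 to V3") and sets the target: "Up to 166 participants might be enrolled to get the target sample of 138 to complete intervention". It says that a 3-point change, if detected, "would be clinically significant enough to warrant clinical implementation as the immediate next step".

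**The concern.** A change score subtracts the whole of the baseline value, which amounts to assuming that V3 PSS rises one point for each point of V1 PSS. If the true slope is below 1, the change score carries avoidable noise: any chance difference between arms in V1 PSS leaks into the estimate in proportion to one minus the slope. ANCOVA estimates the slope from the data and removes that part.

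The protocol ties this estimate to a decision on clinical implementation, despite the pilot label, so its precision matters. The plan also leaves the choice between the change contrast and an optional model open, and prespecification would close it.

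**Working it through.** **Inputs.** Table 1 (PSS, open-label exploratory study): V1 mean 19.8, SD 6.3, n = 103; V3 mean 14.7, SD 6.6, n = 89. Sample Size: SD of change 5.62, difference 3 points, alpha 0.05, 138 completers. Inclusion Criteria: PSS of at least 14. Assumed because not stated: two-sided test and 1:1 allocation (69 per arm).

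**The plan's own figure.** With difference 3 and SD 5.62, a two-sample t-test needs 57 per arm (114 in total) for 80% power. At 69 per arm the power is 87.6%. The stated 138 is therefore more than these inputs require, and lack of power is not the issue here.

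**Slope implied by the pilot.**
- Correlation of V1 and V3: r = (6.3² + 6.6² − 5.62²)/(2 × 6.3 × 6.6) = 0.621.
- Slope of V3 on V1: 0.621 × 6.6/6.3 = 0.651.
- Residual SD: 6.6 × √(1 − 0.621²) = 5.17 (variance 26.75).
- SE of the slope at n = 89: 5.17/(6.3 × √88) = 0.088; 95% CI 0.48–0.82, which excludes 1.

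**Variance cut at the pilot baseline spread.** 1 − 26.75/5.62² = 1 − 26.75/31.58 = 15.3%. Rounding of the two SDs moves this only between 14.1% and 16.5%.

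**Variance cut with the entry threshold.** Take V1 as normal (mean 19.8, SD 6.3) truncated at 14, and hold the slope and residual variance fixed. The V1 SD becomes 4.91. Change variance = (1 − 0.651)² × 4.91² + 26.75 = 2.93 + 26.75 = 29.68, SD 5.45. Cut = 2.93/29.68 = 9.9% (10.2% with the cut-point at 13.5). The protocol does not say whether the threshold is applied at V1 or on the online screening form. If at screening, V1 is only partly truncated, and the cut is 11.0% to 13.4% for an assumed screening-to-V1 correlation of 0.9 to 0.6.

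**Sampling error of the pilot.** Simulating the V1/V3 covariance matrix and the V1 mean at n = 89 gives 95% limits of 2.6–21.2% (truncated) and 4.1–30.9% (untruncated).

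**Sensitivity to the slope (truncated case).**

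| Slope | Variance cut |
|---|---|
| 0.5 in both arms | 18% |
| 0.65 in both arms | 10% |
| 0.8 in both arms | 3% |
| 1.0 in both arms | 0% |
| 0.65 early, 0.8 delayed | 6% |
| 0.65 early, 1.0 delayed | 3% |

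**Effect on the trial (69 per arm, 3 points).**

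| Analysis | SD | Power | 95% CI half-width |
|---|---|---|---|
| Change, SD as stated | 5.62 | 87.6% | 1.89 |
| Change, V1 truncated | 5.45 | 89.5% | 1.83 |
| ANCOVA | 5.17 | 92.3% | 1.74 |

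In the truncated case the interval is 5% narrower (range 1–11%). A change-score analysis would need 138/0.901 = 153 completers to match, about 15 more (138/0.974 = 142 to 138/0.788 = 175, so 4 to 37 more).

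**The same gain seen as baseline imbalance.** The 95% limit of chance imbalance in V1 is 1.96 × 4.91 × √(2/69) = 1.64 points. Multiplied by 1 − 0.651 = 0.349, it shifts the change-score estimate by 0.57 points. At the pilot V1 SD of 6.3 the figures are 2.10 and 0.73 points.

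**The case against.** The strongest reply is that nothing is broken. Randomisation makes the change contrast unbiased, the trial is sized on the SD of change, and on the stated inputs it already has more than its 80% power. The gain is about 3 points of power and 0.09 PSS points of half-width. All of that is true, and it is why this is an improvement and not a correction.

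The size is also uncertain. The correlation is back-solved from SDs on different numbers of people, and the number behind 5.62 is not given. The pilot was single-arm and open-label, enrolled for stress, anxiety or insomnia, and averaged 8.6 sessions against 4 here. No document gives a slope for an untreated arm. These points limit confidence in the amount, not in the direction: a slope of 1 in the delayed arm alone still leaves about 3%, and a slope of 1 in both arms costs one degree of freedom. The 31% upper limit applies only without truncation; with truncation it is 21%.

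The imbalance shift is not a second harm. It is the variance gain in another form, and it is already inside the change-score standard error. A shift of 0.57 is a 95% limit; one SD of imbalance gives about 0.29 (0.57/1.96). ANCOVA removes the shift to the extent that the relation is linear and the slope is well estimated.

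Finally, mean contrasts could come from a baseline-adjusted model. The text specifies none, so one sentence is needed if that is the intention.

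**Conclusion.** The point holds as a recommended improvement. The primary test leaves out a strong covariate that the trial already collects. The expected variance reduction is about 10% if V1 PSS is truncated at 14 and about 15% at the pilot spread, with sampling ranges of 3–21% and 4–31%. It falls to 3–6% if the delayed arm's slope is 0.8 to 1.0. The planned contrast remains valid and adequately powered on the stated inputs. The figures rest on a back-solved pilot correlation, an approximately normal V1 distribution, 1:1 allocation and a two-sided 0.05 test. The direction is secure; the exact size is not.

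**What to change.** In the Analytical Plan, and in the matching sentence of the Abstract, state that the primary analysis is the between-arm difference in V3 PSS adjusted for V1 PSS by ANCOVA. Keep the unadjusted V1-to-V3 change contrast as a sensitivity analysis. Apply the same adjustment to secondary scores that have a V1 value.

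Using change as the dependent variable with V1 PSS as covariate gives the identical treatment estimate. The outcome can therefore still be described as change in PSS elsewhere in the protocol, and one clause saying so keeps the sections consistent.

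The cost is one degree of freedom and the wording in two places. No new data, visits or participant burden are involved.

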If someone has a 10 point or greater increase in depression (as measured by the CES-D) at a follow up visit, they will be given a community resources handout for mental health. The increase is one standard deviation from the typical drop from baseline in the Exploratory Study.

The manufacturer of Cereset Research recently provided the following update regarding safety and regulatory status:

"This technological approach has been used across several branded versions in what are now about 130,000 individuals, with no serious adverse events reported. The device now branded as Cereset, which will be used in research studies as Cereset Research, uses the same core technology and approach as HIRREM, echoing brainwaves in real time as audible tones. Cereset is commercially available as a wellness technology to help manage stress, restore hope, and achieve restful sleep. Cereset software was tested hundreds of times in our office before going to production beginning in October of 2017.

Since then, thousands of sessions using Cereset software have been provided clinically in 25 other offices across the country without any issues. Results thus far have exceeded our expectations.

We previously shared that the HIRREM equipment used at WFSM since 2011, was registered with the FDA as a Class 2 device under regulation number 21 CFR 882.5050 (biofeedback device), and was thus exempt from FDA 510(k) pre-market notification procedures. Based on the same core technology, with a well-documented, extremely favorable risk profile for this approach, the same applies for Cereset. Importantly, Cereset now falls under more recent FDA guidance provided in a document issued on July 29, 2016, regarding General Wellness: Policy for Low Risk Devices. As a low-risk, general wellness device, Cereset is exempt from FDA regulation. Versions of Cereset Research are currently being used as part of IRB-approved research studies at the Uniformed Services University for Health Sciences, and Womack Army Medical Center, as well as at WFSM (as HIRREM-SOP)." ([name], CEO, Brainstate Technologies/Cereset, February 10, 2019, personal communication).

Participant Compensation:

Participants in this research project will not receive any monetary compensation.

Data and Safety Monitoring:

The principal investigator will be responsible for the overall monitoring of the data and safety of study participants. The principal investigator will be assisted by other members of the study staff.

Any collected patient identifying information corresponding to the unique study identifier will be maintained on a separate master log. The master log will be kept secure, with access limited to designated study personnel. Following data collection subject identifying information will be destroyed at the earliest opportunity, consistent with data validation and study design, producing an anonymous analytical data set. Data access will be limited to study staff. Data and records will be kept locked and secured, with any computer data password protected.

Reporting of Unanticipated Problems, Adverse Events, or Deviations:

Any unanticipated problems, serious and unexpected adverse events, deviations or protocol changes will be promptly reported by the principal investigator or designated member of the research team to the IRB and sponsor or appropriate government agency if appropriate.

Appendices

A:

Perceived Stress Scale (PSS) Insomnia Severity Index (ISI) Generalized Anxiety Disorder 7-Item (GAD-7) Center for Epidemiological Studies Depression Scale (CES-D) PTSD Checklist for Civilians (PCL-C) Fatigue Severity Scale (FSS) Quality of Life Scale (QOLS) Interpersonal Support Evaluation List (ISEL-12) Multiple Ability Self-Report Questionnaire (MASQ) Depression, Anxiety, and Stress Scale (DASS-21) EQ-5D Self-Report Health State Question World Health Organization's Heath and Work Performance Questionnaire (HPQ) *Workplace healthcare utilization, missed/medical appointments, etc.

B: COVID-19 Healthcare Worker Study - Screening Video

C: Handout for Study Participants – "Process and Study Details"

D: Eligibility Screening Form

E:

Study Coordinator Email Script Study Coordinator Data Collection Forms Behavioral Health Resource List References:

- Balestroni, G., & Bertolotti, G. (2012). [EuroQol-5D (EQ-5D): an instrument for measuring quality of life]. *Monaldi Arch Chest Dis, 78*(3), 155-159. doi:10.4081/monaldi.2012.121
- Bastien, C. H., Vallieres, A., & Morin, C. M. (2001). Validation of the Insomnia Severity Index as an outcome measure for insomnia research. *Sleep Med*, *2*(4), 297-307. doi:S1389945700000654 [pii]
